7.6 Protected Health Information (PHI)

7.6.1 Does this research involve the use of PHI?	 Yes	 No
--------------------------------------------------	------------------------------	----------------------------------------

If Yes, and subjects will provide written consent to participate in this study, a [HIPAA Authorization](#) should be signed.

If Yes, and you are requesting a waiver of documentation of consent, you should also submit a request for [waiver of HIPAA Authorization](#).

7.7 Compensation

Per Department of Defense guidance, participants will not receive incentives.

Section 8: Experimental Plan

8.1 Equipment

DISTRIBUTION C: Distribution authorized to U.S. Government agencies and their contractors (administrative). Other requests for, or further releases of this document, shall be referred to
[name].

Improving Resiliency in U.S. Air Force Healthcare Personnel
AFRL IRB APPROVED 1 SEPTEMBER 2020

N/A

Section 9: Risk/Benefit Analysis

9.1 Benefits

The SMART training provides short, everyday individual practices, which have been shown to increase individual's resilience in past research with healthcare personnel and other participants. However, the effectiveness of the training has not been evaluated in military personnel. The information learned from this study may help demonstrate if the training is effective in increasing the resilience of military personnel.

9.2 Risks

There are no known risks to participating in this study. It is possible a participant's reflection on past experiences or memories during or after the SMART training may be uncomfortable. Due to this possibility, all participants will be provided contact information for seeking confidential mental health support through local resources or Military One Source.

Section 10: Statistical Consideration and Plan

10.1 Sample Size

We have conducted a thorough analysis to determine a sample size for this proposed study using information derived from the available literature (see Background and Significance: Stress Management and Resilience Training). We considered changes in CD-RISC scores, the primary outcome, from baseline to 12 weeks post-intervention after receiving SMART training (efficacy). We assumed a pre-post intervention change in CD-RISC scores of 7.7 ($SD = 8.7$) to be achievable and meaningful.¹⁰ This corresponds to a standardized mean difference between 0.8 and 0.9 SD . Sample size estimates specified a two-tailed alpha error of .05 for either paired or two-sample t -tests or corresponding nonparametric tests (i.e. Wilcoxon signed ranks or rank sum tests) using a range of effect size and power specifications for mean difference.

Based on this analysis, we propose to recruit 120 active duty service members in total. Assuming up to 25% attrition between enrollment and 12 weeks post-intervention follow-up (i.e. a final sample of 90 or 45 per group), this would be sufficient to achieve 90% power to detect a standardized mean difference of 0.5 SD in either a paired t -test or Wilcoxon signed ranks test.

Section 11: Subject Re-Contact

11.1 Do you wish to re-contact participants for possible participation in future research protocols?	 Yes	 No
If Yes, Permission to re-contact participants for future research projects must be sought via a separate re-contact registry. Contact the IR Office.		

DISTRIBUTION C: Distribution authorized to U.S. Government agencies and their contractors (administrative). Other requests for, or further releases of this document, shall be referred to
[name].

Improving Resiliency in U.S. Air Force Healthcare Personnel
AFRL IRB APPROVED 1 SEPTEMBER 2020

Section 12: Samples

12.1 Will this activity involve the use of biological samples/tissue?		 Yes	 No
If Yes, Choose one:		 Identifiable Specimens	 De-identified Specimens
If No, Proceed to Section 13 .			
12.2 How will samples will be provided to the investigator, labeled, stored, maintained or destroyed, etc.?			
N/A			
12.3 Do you wish to use blood, cells, bodily fluids, tissues and/or other identifiable health information and personal identifiers from patient records (medical, research, hospital, etc.) for use in more than one protocol?		 Yes	 No
If Yes, a tissue/health information registry must be approved if you intend to collect and use tissue and/or health information outside of the parameters of a single IRB approved protocol.			
12.4 Will you be shipping ANY bodily specimens?		 Yes	 No
If Yes and your protocol includes shipping of blood or other potentially infectious material (OPIM) , please ensure that the protocol includes a plan for shipment. Additionally, the protocol and transport plan should be sent to Biosurety ([contact]) to ensure that it meets all required regulations.			
12.5 Does your protocol include the manipulation of blood or other potentially infectious material beyond collection and/or direct analysis?		 Yes	 No
If Yes, the protocol must also be submitted to Biosurety ([contact]) for review and approval.			
If No, personnel must complete annual Blood borne Pathogens (BBP) training and the laboratory must have an Exposure Control Plan.			

Section 13: Safety Monitoring

The PI will ensure that mishaps or injuries sustained during research will be reported as required pursuant to AFI 91-204.

- The Principal or Associate Investigator will provide the test subject(s) a short safety briefing explaining what to do in the event of an emergency. Briefing will include where the exits are located, tornado and shelter-in-place locations, and building evacuation assembly location(s). A mishap is an unplanned occurrence, or series of occurrences, that results in damage or injury, as described in AFI 91-204. In the event of a mishap involving government personnel or property, an AF Form 978, Supervisor Mishap Report, will be completed for property damage, or by the injured personnel's supervisor, and returned to the appropriate government safety office within five (5) workdays following the mishap, or notification of the mishap, whichever is earlier.

Established local infection control practices to minimize the risk of SARS-CoV-2 infection will be followed. Possible examples of these practices include:

- Wearing a cloth mask at all times.

DISTRIBUTION C: Distribution authorized to U.S. Government agencies and their contractors (administrative). Other requests for, or further releases of this document, shall be referred to
[name].

Improving Resiliency in U.S. Air Force Healthcare Personnel
AFRL IRB APPROVED 1 SEPTEMBER 2020

- Maintaining physical distancing (6').
- Reducing the number of people in a room to no greater than five at a time.
- Minimizing the number of staff who have “face to face” contact with study participants.
- Washing hands before and after any in person contact with participants.

Section 14: Data Management and Confidentiality

All data will be collected from participants specifically for research purposes. This study will involve minimal impact, risk, and approximately three hours of time commitment for participants.

Participants will be asked to complete a baseline survey and provide phone and e-mail contact information. This information will be collected by paper after consent is provided and manually entered into REDCap™ by an authorized study member. If desired, participants will be provided a web-link to directly enter their information into the REDCap™ system. Participants names, phone numbers, and e-mail contact information will be coded as a protected identifier to prevent unintentional export of the information from the REDCap™ system.

To ensure confidentiality, the collected data will be entered into and stored on the secure REDCap™ server at the University of New Mexico (UNM) Health Sciences Center (HSC) Clinical and Translational Science Center (CTSC). Paper surveys will be maintained in a locked cabinet located in [name] office. No other individuals utilize the same office space. UNM HSC IRB approval is required to use REDCap™ for data collection related to human subjects research. Researchers must provide the approved protocol number and study closure date prior to putting a REDCap™ database or survey into production status. The CTSC's implementation of REDCap™ is not intended to be a long-term repository or warehouse for personal health information, and the PI will be required to provide the study's IRB expiration date. As the expiration date approaches, the system administrator we will contact the [name] for proper disposition of the REDCap™ data.

Participants will be made aware that the SMART course may be provided in a group setting. During any interactive portion of the course, participants may volunteer to provide information, thoughts, and feedback; however, they are not required to provide any information. All follow-up phone calls will be scheduled at a time and location of the participants' choosing. For all baseline and follow-up surveys, participants may choose which items they complete.

All data files used during the data analysis will be password protected. Any printouts from software (e.g. IBM® SPSS® Statistics) will be de-identified. Settings in REDCap™ will be enabled to ensure that only [name] will be able to identify a specific participant and their survey responses based upon a linked number assigned by REDCap™ when the surveys are completed.

Section 15: Data Sharing Plan

Collected data will be stored in the REDCap™ project database hosted by the UNM HSC CTSC Informatics behind the firewall of the HSC. Access from outside of the UNM HSC will require the use of a secure UNM HSC Net ID. [name] and other team members who are employees of the

DISTRIBUTION C: Distribution authorized to U.S. Government agencies and their contractors (administrative).

Other requests for, or further releases of this document, shall be referred to

[name].

Improving Resiliency in U.S. Air Force Healthcare Personnel
AFRL IRB APPROVED 1 SEPTEMBER 2020

UNM HSC will complete the planned data analysis. Printed study documents will be locked a filing cabinet located in [name] office.

After the study is completed, the de-identified data may be placed in a central storage location at the UNM HSC. Identifiers (i.e. name, phone and e-mail contact information) will be removed from the data and non-identifiable data could be used for future research studies or distributed to another investigator for future research studies without additional informed consent from participants. The purpose is to make study data available to other researchers.

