Variables and Measures. Baseline data will be collected from each participant prior to the delivery of the intervention. The baseline survey will include nine demographics questions to attain information for participant age, gender, marital status, race, ethnicity, previous deployment, military grade/rank, duty location, and military job duty (i.e. AFSC). Participants' names and preferred e-mail and phone contact information will be requested. This information is necessary to arrange a follow-up phone call for each participant approximately four weeks after completing the SMART training and to send follow-up surveys via the Research Electronic Data Capture System (REDCap™; see Intervention) at weeks 12 and 24 (if applicable) after participants complete SMART. The baseline and follow-up surveys will also include the Connor Davidson Resilience Scale (CD-RISC)²⁰⁻²¹, Perceived Stress Scale (PSS)²²⁻¹³, Generalized Anxiety Disorder Scale (GAD-7)²⁴, and five-item Quality of Life (QoL) measures.²⁵

Change in resilience scores on the CD-RISC will be the primary endpoint of the study; secondary endpoints include changes in PSS, GAD-7, and the five-item QoL measure. Although stress, anxiety, and QoL are not primary outcome variables in this study, a decrease in stress and anxiety and an increase in QoL have been reported in past studies by participants who completed SMART, in addition to changes in resilience. Including the PSS, GAD-7, and QoL measure will offer an additional opportunity, with minimum response burden, to compare participant outcomes from this study with outcomes reported in previous studies.

Connor Davidson Resilience Scale. The CD-RISC has been utilized to measure service member resilience in multiple studies.^{21, 26-30} The 25-item scale was developed from multiple studies of the characteristics of resilient individuals.⁶ Respondents can answer each item using a five point Likert scale ranging from not true at all (0) to true nearly all the time (4).⁶ A total CD-RISC score is calculated by summing the score of all 25 items for a total possible score of 100, with a higher score reflecting a greater level of resilience.⁶

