Study team members will verify participant data has been entered correctly. Participant e-mail and phone contact information will be used to schedule a follow-up phone call two weeks after completing the SMART training (see intervention). Participants' e-mail contact information will be used to send follow-up surveys through REDCapTM. Each survey will take approximately 10 to 15 minutes for participants to complete. If the participant does not respond to the initial REDCapTM invitation, a maximum of three e-mail reminders (one reminder per week after the initial e-mail is sent) will be sent to complete the survey.³⁷ If a participant does not complete the survey after all e-mail requests have been sent, a study team member may call the participant to verify their e-mail information and offer to assist the participant with accessing the survey. Because participants' demographic information will be associated with an individual's contact information in REDCapTM, demographic information will not be requested as part of the surveys at weeks 12 or 24. All data will be de-identified prior to exporting the data for analysis.

Data Analysis. IBM[®] SPSS[®] Statistics (version 26) and R (survey package, version 3.61) will be used for the statistical analysis. Initial analysis will include descriptive statistics, including means or medians, frequencies and percentages, as appropriate, to characterize demographic status, military grade, duty location, military occupation, and previous deployment status. Cronbach's α will be calculated for each multi-item scale.

The objectives of our analysis include testing and estimating the efficacy of the intervention by comparing pre-post intervention changes (improvements) in the outcome measurements of interest. Analyses will be reported as point estimates with 95% confidence intervals and appropriate estimates of effect size. In this analysis, both the VTC and on-line groups will be analyzed separately and scores will also be pooled together to test for overall intervention effects.

To better understand factors that can impact the intervention effects, we will conduct regression models on the pre-post intervention difference while controlling for demographic characteristics,

DISTRIBUTION C: Distribution authorized to U.S. Government agencies and their contractors (administrative). Other requests for, or further releases of this document, shall be referred to
[name].

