Improving Resiliency in U.S. Air Force Healthcare Personnel
AFRL IRB APPROVED 1 SEPTEMBER 2020

AFSC, and previous deployment. We will also take into consideration potential clustering effects among the participants from the same organizational unit using random effects (e.g. in regression models).

Changes in resilience, stress, anxiety, and QoL over time will be assessed by separately analyzing changes from baseline to week 12 and to week 24. A joint analysis of the longitudinal trend over the three time points at baseline, 12-week, and 24-week will be completed. We will also consider a joint analysis of resilience, stress, anxiety, or QOL, as well as, analysis for subscales of any specific domain of interest.

Section 7: Subject Selection

7.1 Do you plan to target a specific population for your study? Yes No

If Yes, please complete 7.2

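### The week-12 CD-RISC change is planned on people with both scores, and no planned result uses, or tests the effect of, the up to 25% who are lost

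*Combined protocol and SAP*

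**What the plan says.** Section 6.1 (Variables and Measures) states: "Change in resilience scores on the CD-RISC will be the primary endpoint of the study". Section 10.1 sets the interval: "from baseline to 12 weeks post-intervention after receiving SMART training (efficacy").

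Section 10.1 gives the enrolment target ("we propose to recruit 120 active duty service members in total") and then the loss: "Assuming up to 25% attrition between enrollment and 12 weeks post-intervention follow-up (i.e. a final sample of 90 or 45 per group"). It describes that final sample as "sufficient to achieve 90% power to detect a standardized mean difference of 0.5 SD in either a paired" t-test or Wilcoxon signed ranks test.

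Section 6.1 (Data Analysis) gives the aim as "testing and estimating the efficacy of the intervention by comparing pre-post intervention changes (improvements) in the outcome measurements of interest", by delivery group and pooled, with regression models on the pre-post difference. It adds: "A joint analysis of the longitudinal trend over the three time points at baseline, 12-week, and 24-week will be completed". No model is named for that joint analysis, it is not made the primary result, and the handling of missing scores is not stated.

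Against non-response, 6.1 (Procedures) provides up to three weekly e-mail reminders and then a possible telephone call. The documents give no imputation, weighting, sensitivity analysis or comparison of people with and without follow-up.

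**The concern.** A paired test, or a regression on a difference, needs two scores from the same person. At the planned ceiling, 30 of 120 enrolled people would have a baseline CD-RISC score that plays no part in the week-12 result. The objective in 5.2 concerns Air Force healthcare personnel, not those among them who finish training and return a survey three months later.

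The effect is a change within trained people. In a comparison with an untrained arm, selective loss of the same kind in both arms could partly cancel. Here all of it passes into the estimate. Section 4 also says that the result will be read against gains reported in civilians, so the size of the gain matters as well as its significance.

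**Working it through.** **Inputs.** From 10.1: 120 enrolled, up to 25% lost, change 7.7 with SD 8.7, detectable effect 0.5 SD, two-sided alpha 0.05. From the CD-RISC description in 6.1: SD 11 in a large Air Force sample. Assumptions not in the documents: SD 11 at both times, normal scores, and the loss splits below.

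**1. The plan's own figures.** 120 × 0.75 = 90, or 45 per group. 7.7/8.7 = 0.885, which agrees with the stated 0.8 to 0.9 SD. A paired t-test with n = 45 and effect 0.5 has noncentrality 0.5 × √45 = 3.35 and power 90.7%. Wilcoxon by simulation gives 89.4%. So the 90% holds for each group of 45; for the pooled 90, power is 99.7%. The arithmetic is sound.

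**2. Responders against all enrolled.** Mean over all enrolled = 0.75 × responder gain + 0.25 × non-responder gain. With a responder gain of 7.7:

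| Non-responder gain | Mean over all 120 | Responder mean too high by |
|---|---|---|
| 7.7 | 7.70 | 0 |
| 3.85 | 6.74 | 0.96 |
| 0 | 5.78 | 1.93 |
| −2 | 5.28 | 2.43 |

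A responder gain of 4.35 (0.5 × 8.7) becomes 0.75 × 4.35 = 3.26 if non-responders did not change.

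**3. Loss that depends on baseline.** The implied baseline to week-12 correlation is 1 − 8.7²/(2 × 11²) = 0.69, so the slope of change on baseline is 0.69 − 1 = −0.31. Suppose 35% are lost below the median and 15% above. Responders are then shifted by √(2/π) × (0.85 − 0.65)/2 / 0.75 = 0.798 × 0.133 = 0.106 SD. Their baseline mean is 11 × 0.106 = 1.17 too high, and the paired change is off by −0.313 × 1.17 = **−0.37**. Simulation agrees: paired mean 7.33 against a true 7.70, and 7.69 from a regression using all baselines. At 40%/10% the error is about 0.55.

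**4. Loss that depends on the change itself.** With the same split by below-average or above-average change, the paired mean is off by 8.7 × 0.106 = **+0.93** (simulation 0.91 to 0.92). Change and baseline correlate at −0.313 × 11/8.7 = −0.40, so responders' baselines are only 0.40 × 11 × 0.106 = 0.46 too low. A model using all baselines therefore corrects only 0.313 × 0.46 = 0.14 and leaves about **+0.78**.

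**5. Chance of a significant increase when the true change is zero** (nominal 2.5%), pooled, under step 4. The paired standard error is about 8.65/√90 = 0.91. Then 0.93/0.91 = 1.02, and P(Z > 1.96 − 1.02) is about 17%. For the model, the standard error is √(8.7² × (1 − 0.40²)/90 + 0.313² × 11²/120) = 0.90. Then 0.78/0.90 = 0.87, and P(Z > 1.09) is about 14%. Simulation gives about 17% and 13 to 14%; at 40%/10% it gives 33% and 26%.

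**6. How low non-responders must go for the lower 95% limit to reach zero.** Solve 0.75 × gain + 0.25 × g = half-width.
- Half-width from responders only: 1.987 × 0.75 × 8.7/√90 = 1.37.
- Half-width as if all 120 were observed: 1.98 × 8.7/√120 = 1.57.
- At 7.7: g = (1.37 − 5.775)/0.25 = −17.6, or (1.57 − 5.775)/0.25 = −16.8.
- At 4.35: g = (1.37 − 3.26)/0.25 = −7.6, or (1.57 − 3.26)/0.25 = −6.8.

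**The case against.** **Direction.** A reader might infer that the planned analysis inflates the gain. The documents do not support that. Nothing in them says that people who gained less answer less often. If people who are doing well stop answering, the bias is downward, and the baseline-dependent case in step 3 also runs downward. The splits are assumptions. This objection stands, and the point is therefore stated without a direction.

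**Remedy.** A likelihood-based model assumes that data are missing at random. Where loss depends on benefit, it removes little (0.93 to 0.78). This also stands, and it is why the sensitivity results are needed as well as the model.

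**Significance.** At the plan's own effects the conclusion is not fragile. Even with non-responders at zero change, 5.78 and 3.26 are about 7 and 4 times 8.7/√120 = 0.79. The 17% figure applies only if the true change is zero and loss follows the assumed split.

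**What the 25% is.** A reader might take all 30 people as survey non-responders. Section 10.1 counts loss from enrolment, and surveys are timed from completion of SMART. The 30 therefore include people who never finish training and have no defined week-12 date. The documents do not give the division.

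**What the text fixes.** The paired test is named only in the sample-size section, and 90 is the figure at the loss ceiling. That is fair, but regression on the pre-post difference in 6.1 implies the same people. The joint analysis could use baseline-only people if fitted by likelihood, but the plan does not say so. The reminders and call may reduce loss; they do not show what the remaining loss could do.

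**Conclusion.** The point holds as a gap in the analysis, not as a demonstrated inflation. The week-12 change rests on people with both scores. Attrition is met by extra recruitment and reminders, and no planned result uses the baseline-only people for that estimate or shows how far they could move it.

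Under the assumed 35%/15% splits the paired mean is wrong by about 0.37 points downward or 0.9 upward, depending on what drives the loss. These sizes scale with actual loss and rest on SD 11, change SD 8.7 and the full 25%.

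Significance is robust at the plan's effects. Non-responders would have to average about −17 to −18 points at a responder gain of 7.7, or −7 to −8 at 4.35. The reported size of the gain is what is exposed. The change is worth making before outcomes are seen.

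**What to change.** In 6.1 Data Analysis:

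1. Make the main week-12 estimate the week-12-minus-baseline contrast from a likelihood-based repeated-measures model, with time as a category, unstructured covariance and the planned unit random effect, fitted to everyone with a baseline score. Specify the joint three-time-point analysis in this form. Keep the paired test as supportive.
2. Because that model assumes data are missing at random, pre-specify two sensitivity results: people without a week-12 score set to zero change, and the mean change among them at which the lower 95% limit for all enrolled reaches zero.
3. Tabulate baseline scores of people with and without a week-12 score, separating those who did not complete SMART from those who completed it but did not answer.

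The cost is plan wording and a few hours of programming on data already to be collected, with no new participants or contacts. The downside is that the sensitivity figures may look less favourable than the responder estimate.
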